2.3.2 Safety of DHA Supplementation In Other Autoimmune Disorder Studies

Observations about omega-3 supplementation have been made in other autoimmune disorder studies. As recently reviewed, fish oil has been used as an anti-inflammatory agent in other chronic autoimmune disorders such as rheumatoid arthritis, systemic lupus erythematosus and Crohn's disease [62]. No significant adverse effects have been reported in multiple studies in other autoimmune diseases, and in some cases biological and/or clinical benefit has been seen [63-71].

2.3.3 Safety of DHA Supplementation in Non-Autoimmune Disease

Further support for the proposed n-3 supplementation comes from several large studies showing positive health and safety outcomes. In studies of cardiovascular disease endpoints, DHA has shown some efficacy [72-76]. DHA was well tolerated in all these studies. Newly diagnosed individuals with T1D given fish oil had mean HbA1c levels in the normal range after nine months of supplementation. Some studies using DHA to treat bipolar disorder have safely used ten times the amount of DHA proposed for use in this study [77].

2.4 Dietary Consumption of DHA

Numerous studies of omega-3 fatty acids have been done in a variety of clinical states including studies involving pregnant and lactating mothers. There are no studies that suggest any adverse effects from supplementing with DHA as a source of n-3 fatty acid. DHA provides important benefits during pregnancy, but because of recent contamination concerns, fish consumption during pregnancy has been decreasing. This decrease in fish consumption during pregnancy has been occurring as the rate of diabetes has been increasing. Farm-raised fish that consume corn or grain do not have the same n-3 content as fish that consume algae or other marine sources of food. Fish and other n-3 fatty acids were previously a primary source of DHA during pregnancy and to the developing infant during lactation. The modern diet has a ratio of pro-inflammatory n-6 fatty acids to anti-inflammatory n-3 fatty acids that has changed significantly over only a few decades. The impact of this change may be most pronounced during fetal development and infancy. The FDA has granted GRAS (Generally Recognized as Safe) status to DHA and it has been approved for addition to infant formulas. Several infant formulas containing DHA are now commercially available in the U.S.

2.5 Biochemical Islet Autoantibody Development in T1D Genetic Risk Individuals

The outcomes of interest for this protocol are the development of T1D and the presence of biochemical islet autoantibodies. There is a significant increase in the risk of diabetes with the number of biochemical islet autoantibodies present, comparing zero, one, two, and three autoantibodies (P<0.0001, log-rank test) by Cox regression analysis [78]. This is independent of which biochemical islet cell autoantibodies and age. For relatives of T1D patients having two or more of these biochemical islet autoantibodies present, the risk of diabetes within 3 years was 39% (95% CI, 27-52) and the risk within 5 years was 68% (95% CI, 52-84). Relatives with all three biochemical islet autoantibodies had a risk of developing T1D within 5 years estimated to be 100% [79].

3 Study Design

3.1 Overview

The study is a multi-center, two-arm, randomized, double-masked, controlled clinical trial. The total length of this pilot feasibility trial will be two years (one year of recruitment and one year of follow-up to assess feasibility) with the possibility of up to another 2 years of follow-up if transition time is needed for enrollment into a full-scale NIP study.

3.2 Inclusion Criteria

Potential participants must meet the following inclusion criteria:

Pregnant mothers are eligible for enrollment into this study if they:

- 1. have T1D or the child's father, or a full or half-sibling of the child has T1D
- 2. are 18 years of age or older
- 3. are in their third trimester of pregnancy (i.e. gestation is 24 weeks or longer)
- 4. have given written informed consent and HIPAA authorization
- 5. are willing to be assigned to either treatment group

Infants are eligible for enrollment into this study if they:

- 1. are less than or equal to six months (i.e. ≤ 182 days from the date of birth) of age on the date of randomization
- 2. are found to be at risk for type 1 diabetes because they have a mother, father or full or half-sibling with T1D AND
 - have a HLA DR3 or DR4 allele OR
 - have another 1st or 2nd degree relative with T1D (multiplex family)
- 3. have a parent or legal guardian who has given written informed consent and HIPAA authorization
- 4. have a parent(s) or legal guardian(s) who are willing for their baby to be assigned to either treatment group

3.3 Exclusion Criteria

Potential participants must **not** meet any of the following exclusion criteria:

Pregnant mothers are NOT eligible for enrollment into this study if they:

- 1. have any condition the investigator believes will put the mother or her fetus at an unacceptable medical risk for participation in this study
- 2. have a known complication of pregnancy causing an increased risk for the mother or fetus prior to entry into the study

- 3. have previously had multiple (2 or more) pre-term births (<36 weeks)
- 4. will take omega-3 fatty acid supplementation or will provide omega-3 fatty acid supplementation to her infant independently during the study
- 5. have diabetes and a known HbA1c greater than 9% at anytime during the pregnancy

Infants are NOT eligible for enrollment into this study if they:

- 1. have any condition the investigator believes will put the infant at an unacceptable medical risk for participation in this study
- 2. have a mother with a condition the investigator believes will put her or the infant at an unacceptable medical risk for participation in this study
- 3. have a nursing mother who will take omega-3 fatty acid supplementation or a parent or legal guardian who will provide supplementation to his/her infant independently during the study (if infant entered prenatally, this exclusion criteria is assessed only once when the pregnant mother entered the study)
- 4. have a protective HLA allele (DQB1*0602 or DRB1*0403)
- 5. were born prior to 36 weeks gestation or require a pre-term infant formula

3.4 Screening and Enrollment

3.4.1 Pregnant Women

Pregnant women may be referred to the study by their physician or recruited at participating TrialNet study sites. All sites will comply with HIPAA regulations. Screening will consist of a clinic visit to be conducted after the 24th week of gestation for the pregnant woman. The pregnant woman will be asked if she would be interested in participating in the research project. Those indicating interest will be referred to one of the Investigators or Study Coordinators for a description of the study. Essential components of the presentation are that the parent(s) are being invited to participate in research, participation in the study is voluntary, and participation may be ended at the parent(s)' request. TrialNet research personnel will provide the parent(s) with a full description of the study, the inclusion and exclusion criteria, the procedures involved, the study groups and the randomization process, time commitments and the schedule of follow-up visits. A screening data form will be completed.

Pregnant women without diabetes can be enrolled after screening with no laboratory tests required if they meet eligibility criteria. Pregnant women with diabetes will need an HbA1c test as part of eligibility screening prior to randomization.

Supplementation with the study substance (DHA or control) will begin immediately after randomization, and continue at least until the HLA type of the infant is known. At that time, infants will either be enrolled into the study as continuing infants and continue taking the study substance, or be deemed ineligible for continuation in the study. The consented mother will receive a TrialNet identification number, and a baseline data collection form will be completed. To determine HLA eligibility status for the infant, a sample will be obtained either at birth by cord blood collection, or by a heel stick collected 2 to 28 days after the birth.

3.4.2 Infants of mothers enrolled during pregnancy

Infants with mothers who started on supplementation during the third trimester of pregnancy are screened for continued participation in the study. This process requires laboratory tests using cord blood collected from the placenta at birth, or by a heel stick collected 2 to 28 days after the birth of the infant. A screening data collection form will be completed, and the infant's blood sample will be analyzed for HLA determination. The screening process will be completed within approximately four weeks of birth. Infants who have either a single 1st degree relative with T1D and higher risk HLA genes, or infants with one 1st degree relative and another 1st or 2nd degree relative with T1D (a multiplex family) will be enrolled in the study. If the infant has a protective allele, he/she will not be eligible for the study. In the case that multiple infants within the same family are eligible, either simultaneously (e.g. twins), or successively (e.g. siblings), all may be entered into the study. Eligible infants born to mothers entering in the study when pregnant will continue in the study with the same treatment group assignment as the first prenatal infant. Nursing mothers and infants will continue taking the study substance while eligibility is being determined.

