3.7 Treatment Groups

3.7.1 Description of Treatment Groups and Treatment Modalities

The sample of 90 eligible participants will be randomly assigned in approximately equal numbers to the two groups (experimental treatment or control group). About half (forty-five) of the participants will receive the docosahexaenoic acid (DHA) study substance daily, and half (forty-five) will receive the control.

Depending on their mode of intake participants will receive the study substance either indirectly through the placenta or breast milk, or directly in the form of infant formula or the contents of capsules mixed in with food, or in a form suitable for toddler consumption. Comparisons will be made between groups receiving DHA supplementation (experimental treatment) versus the control as described in Tables 1 and 2. Group assignment will be random and masked.

The study substance will be given to the infant in one of the following ways for a minimum duration of 12 months from the date of birth (if entered prenatally), or date of randomization (if entered post-partum). The study substance is given in one of the following ways (Tables 2 and 3).

During pregnancy:

1. Mothers enrolled during pregnancy take 4 capsules a day until the infant's HLA type is determined.

[After birth, if the infant does NOT have the higher-risk genes (and did not pre-qualify by having multiple family members with T1D) or has a protective allele, the family will be withdrawn from the study.]

After the HLA type is known from birth until 1 year of age:

Nursing mothers will be provided with study formula or capsules to use if nursing is discontinued or the infant is weaned.

- 1. For mothers that are nursing:
 - a. The mother takes 4 capsules/day until she stops nursing or until baby is 12 months old.
 - b. At 6 months old the infant is given 1 capsule/day and the nursing mother continues to take 4 capsules/day. Assume that the infant will start transitioning to foods at this time.
- 2. For infants that are taking study substance:
 - a. At 0 to 6 months old the infant is given the study formula.
 - b. At 6 to 12 months old, if the infant is taking more than 32 oz/day of the study formula, no additional study capsules will be mixed in the food.
 - c. At 6 to 12 months old if the infant is taking less than 32 oz/day but more than 16 oz/day of the study formula on average over the previous week, the parent will give the content of 1 study capsule per day to the infant by mixing in food.

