 - d. At 6 to 12 months old if the infant is taking less than 16 oz/day of the study formula on average over the previous week, the parent will give contents of 2 study capsules per day to the infant by mixing in food.
- 3. For infants partially breastfeeding and taking infant formula (study formula):
 - a. The nursing mother follows the schedule as if she is exclusively nursing.
 - b. The infant follows the schedule as if he/she is exclusively taking the study formula according to infant age.

After 1 year of age through study end:

- 1. Transition all infants at 12 months old to mixing the contents of 2 capsules/day in food or the equivalent provided in a suitable form for toddler consumption.
- 2. The nursing mother stops DHA/control capsule supplementation.

Subject	DHA Supplementation group
Pregnant Mother	800 mg/day
Nursing Mother	800 mg/day
Nursing Infant	\cong 120-400 mg/day (via the mother)
Formula-fed Infant ¹	≅ 120-400 mg/day
Toddlers aged 1-3 yrs	≅ 400 mg/day

Table 2. Approximate Amount of Nutrient Intake and Assessment

¹The control formula will contain about one-third of the amount of DHA as the intervention formula.

Table 3. Summary of Study Substance Intake for Mother and Baby

			Baby's A	\ge	
	3 rd trimester to Birth		4 to 6 mos	6 to 12 mos	12 to 36 months of age or end of study
Mother					
Pregnant	4 caps/day	NA	NA	NA	NA
Exclusively nursing	NA	4 caps/day	4 caps/day	4 caps/day	0
Partially nursing and providing study formula	NA	4 caps/day	4 caps/day	4 caps/day	0
Baby					
Nursing	NA	0	0	1 cap/day	2 caps/day
Partially nursing and taking study formula or Exclusively taking study formula	NA	Study Formula	Study Formula	32 oz of Study Formula 16 to 32 oz of Study Formula plus 1 cap/day or ≤16 oz of Study Formula plus 2 cap/day	2 caps/day

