4.2 Screening and Enrollment Visit Schedule

4.2.1 Entry Point A: Screening and Enrollment During Pregnancy

4.2.1.1 Pregnant Woman (Prenatal Infant) Screening and Enrollment:

Informed Consent Process

Specimen Tests:

- If woman has diabetes (type 1, type 2, or gestational): local HbA1c to determine eligibility
- Baseline islet autoantibodies, RBC fatty acid levels, inflammatory mediators levels, Vitamin D level, and CRP level
- Residual specimens for storage (if available)

Data Collection Procedures:

 Assessment of concomitant medications including vitamin and supplementation record, medical history, family history and food frequency questionnaire

If the pregnant woman meets eligibility criteria to participate:

- Unborn infant(s) randomized to the experimental treatment or control group
- Study capsules dispensed.
- Cord blood kit provided to parent with instructions to collect and ship

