4.2.1.2 Infant Screening (Infant of Participating Pregnant Woman)

a. Day of Infant Delivery:

Specimen Tests (if cord blood available):

- HLA to determine eligibility
- Baseline islet autoantibodies, RBC fatty acid levels, inflammatory mediator levels, Vitamin D level and CRP level.
- Residual specimens for storage (if available)

b. Infant (2 to 28 days of age):

Informed Consent Process

Specimen Tests:

Infant:

If cord blood not collected at birth, blood is collected by heel stick for the following:

- HLA to determine eligibility
- Islet autoantibodies
- Residual specimens for storage (if available)

Mother:

- Islet autoantibodies
- Residual specimens for storage (if available)

Data Collection Procedures:

• Limited physical examination, pregnancy and birth history, medical history of infant, medication history, assessment of concomitant medications including vitamin and supplementation record, food frequency questionnaire, family history, and adverse events assessments.

4.2.1.3 Infant Enrollment (approximately 4 weeks after blood collected for HLA typing):

Other Procedures:

- Results of infant's HLA testing discussed with parent(s). Parents are only told if genes are higher or lower risk for type 1 diabetes.
- Authorization to release medical records related to birth
- Study capsules and/or formula collected/dispensed.

Mother Specimen Tests:

- RBC fatty acid levels, inflammatory mediator levels, Vitamin D level, and CRP
- If nursing, breast milk fatty acid levels
- Residual specimens for storage (if available)

Data Collection Procedures:

- Medical history, pregnancy history, birth history, a food frequency questionnaire, assessment of concomitant medications including vitamin and supplementation record, an immunization history, a food introduction history, and adverse events assessments.
- 4.2.2 Entry Point B: Screening After Birth (for mothers not enrolled during pregnancy)

4.2.2.1 Infant Screening (2 days to 5 months of age):

Informed Consent Process

Specimen Tests:

Infant:

- HLA to determine eligibility
- Islet autoantibodies
- Residual specimens for storage (if available)

Mother:

- Islet autoantibodies
- Residual specimens for storage (if available)

Data Collection Procedures:

 Limited physical examination, pregnancy and birth history, medical history of infant, medication history, assessment of concomitant medications including vitamin and supplementation record, food frequency questionnaire, and family history

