Inflammatory mediators	Р	I ^{cb}			N ^B , M ^A		I		Ι		I		I	Ι
Vitamin D	Р	I ^{cb}			N ^B , M ^A		I		I		I		I	I
CRP	Р	I ^{cb}			N ^B , M ^A		I		I		I		I	I
Blood sample collected for storage													I	
Concomitant Medication Assessment (including vitamin and supplement)	Р		M ^A	I, N	I, N ^B , M ^A	I, N	I, N	I, N	I, N	I	I	I	I	Ι
Food Frequency Questionnaire	Р		M ^A	N	N ^B , M ^A	N	N	N	Ν					
Food Introduction History					I	I	I	I	Ι	Ι	I	I	I	Ι
Immunization Record					I		I		I		I		I	Ι
Provide DHA or Control (capsules or infant formula)	Р		I, M ^A		I, N	I, N	I, N	I, N	I, N	Ι	I	Ι	I	 *
Adverse Events Assessments			I, M ^A		I, M ^A	I, N	I, N	I, N	I, N	Ι	I	I	I	Ι

P: Mother who entered her infant prenatally (she entered during pregnancy)

M: Mother (includes non-nursing and nursing mothers)

I: Infant

N: Nursing mother

*Up to 3 years of age ^A Entry A: The mother entered during pregnancy ^B Entry B: The infant entered after delivery Schedule of Assessments does not reflect when mother or infant attends the visit but what information is collected regarding mother and/or infant. Infants are not required to attend the infant enrollment visit or visits when they are 3, 9, 15, 21 months old.

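### For prenatally entered families the protocol contradicts itself on study substance between birth and infant enrolment, and no passage supplies study formula at or before birth

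*Protocol*

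**What the plan says.** **Infants.** Section 3.4.2 covers the period before the HLA result: "Nursing mothers and infants will continue taking the study substance while eligibility is being determined". Section 3.7.1 measures the infant's minimum 12 months of study substance from the date of birth when entry was prenatal, and its item 2a gives study formula from 0 months. The heading above those infant rules is "After the HLA type is known from birth until 1 year of age".

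**Mothers.** Section 3.4.1 has supplementation start at randomization and "continue at least until the HLA type of the infant is known". Section 3.7.1 says "Mothers enrolled during pregnancy take 4 capsules a day until the infant's HLA type is determined", with no condition on nursing. Section 3.4.2 names nursing mothers and infants only. In "Table 3. Summary of Study Substance Intake for Mother and Baby", the row for the pregnant woman is not applicable after birth, two rows cover nursing mothers, and no row covers a mother who is not nursing.

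**Supply.** At the pregnancy visit, section 4.2.1.1 lists "Study capsules dispensed" and no formula. Section 4.2.1.2, covering delivery and the 2 to 28 day visit, lists no dispensing. Section 4.2.1.3, infant enrolment, is the first visit section to name formula: "Study capsules and/or formula collected/dispensed". It falls about 4 weeks after the HLA sample. In Appendix A the row "Provide DHA or Control (capsules or infant formula" is marked for the infant and for the prenatally entered mother in the 2 to 28 day column, and is blank at birth. The key to that table defines mother as including non-nursing mothers.

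**The concern.** A site has to know three things for the weeks after delivery: whether a formula-fed infant takes study formula before the HLA result, whether a mother who is not nursing keeps taking capsules, and when formula reaches the home. The protocol answers each in more than one way.

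A site that follows the 4.2.1 visit lists literally cannot carry out 3.4.2 for a formula-fed infant, because it has handed out no formula. Such an infant would be fed non-study formula in either arm, so randomization creates no difference in formula DHA for that time. An infant who is partly nursed may still receive a contrast through the milk.

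Objective 2 asks that at least 90% of families take the study substance as directed. For this interval the direction itself is unclear, so compliance cannot be scored consistently.

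**Working it through.** The protocol states no length for this interval, so there is no figure to reproduce. The length can be derived from its visit timings.

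**Inputs**
- HLA sample: cord blood at birth (day 0) or heel stick on days 2 to 28 (3.4.1, 3.4.2).
- Infant enrolment: about 4 weeks, taken as 28 days, after the HLA blood is collected (4.2.1.3).
- End of screening: within about four weeks of birth (3.4.2).
- Provision row: marked at the 2 to 28 day visit (Appendix A).

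**Days from birth to first study formula**

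| Passage followed | Calculation | Days | Weeks | Share of first 182 days |
|---|---|---|---|---|
| 4.2.1, cord blood | 0 + 28 | 28 | 4.0 | 28/182 = 15% |
| 4.2.1, earliest heel stick | 2 + 28 | 30 | 4.3 | 30/182 = 16% |
| 4.2.1, latest heel stick | 28 + 28 | 56 | 8.0 | 56/182 = 31% |
| 3.4.2 screening timing | about four weeks | about 28 | about 4 | about 15% |
| Appendix A | visit on day 2 to 28 | 2 to 28 | 0.3 to 4.0 | 1% to 15% |

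As a share of the first year, 28 and 56 days are 28/365 = 8% and 56/365 = 15%.

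The timings also conflict with each other. A heel stick on day 28, which 3.4.2 permits, plus the 4 weeks of 4.2.1.3 gives day 56. The same section 3.4.2 ends screening about four weeks after birth.

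**Contrast affected.** Table 1 gives 10.2 mg DHA per ounce in the experimental formula and 3.4 mg in the control formula, a planned contrast of 10.2 − 3.4 = 6.8 mg per ounce. On non-study formula the assigned contrast is zero. A cumulative loss would be 6.8 mg × ounces per day × days, but the protocol gives no intake for the first weeks of life, so no total is calculated here.

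**Non-nursing mother, passages side by side**
- 3.4.1: continuation at least to the HLA result.
- 3.7.1: capsules until the HLA result, no nursing condition.
- Appendix A: provision at 2 to 28 days to a category that includes non-nursing mothers.
- 3.4.2: names nursing mothers only and does not mention the others.
- Table 3: no row for her after birth.

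Three passages point to continuation, one is narrower and one is silent.

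**The case against.** **The longest gap is only one reading.** A reader might infer from 4.2.1 that formula-fed infants spend 4 to 8 weeks off study formula. The documents do not support that as a general statement. It holds only if the Appendix A row is disregarded, and its upper end conflicts with the four-week screening limit in 3.4.2. Under Appendix A the wait is 2 to 28 days. This objection stands, and the gap has to be given as a range by passage.

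**A mother who stops at birth does not thereby follow Table 3.** That reading is tempting because the pregnant row ends at birth. But the row describes pregnancy and is not a stopping rule, and the table simply omits the non-nursing mother. What remains is an omission in Table 3 and narrower wording in 3.4.2, set against three passages that imply continuation.

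**The heading in 3.7.1 may be only awkward.** It contains both the HLA condition and a start at birth, and item 2a starts at 0 months. Ambiguity is a fair description, but a site needs one meaning.

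**Consequences for the endpoints are not shown.** Infant red-cell fatty acids are measured at 6 and 12 months, any gap falls on both arms, and the protocol already accepts infants randomized up to 182 days of age. A reader might also infer a loss in grams of DHA or a count of affected families. Both would need assumed figures for newborn intake and early formula use. No effect on Objectives 4 or 5 is claimed.

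**Earlier supply might be implied.** The line in 4.2.1.3 speaks of collecting as well as dispensing. The same line appears in 4.2.2.2 for infants randomized only at that visit, so it does not show that formula was handed out before.

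**Supply details could sit in an operations manual.** The protocol itself fixes dispensing visit by visit and again in Appendix A, and the two disagree.

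**Conclusion.** The contradiction is in the text and should be resolved. Section 3.4.2 has infants on study substance while eligibility is pending. The 4.2.1 visit lists supply no formula until infant enrolment, Appendix A supplies study substance at 2 to 28 days, and no passage supplies formula at or before birth.

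Depending on the passage followed, the time without study formula is about 0.3 to 4 weeks, about 4 weeks, or 4 to 8 weeks. For that time there is no assigned between-arm difference in formula DHA for a formula-fed infant. The rule for non-nursing mothers is incomplete rather than flatly contradictory.

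The range assumes that about 4 weeks means 28 days, and that the Appendix A entries sit in the columns their order suggests, since the table was read from a PDF. The provision row does not say which product the infant receives at 2 to 28 days; formula is inferred because neither 3.7.1 nor Table 3 gives infants capsules before 6 months. The number of families affected cannot be derived from the protocol.

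**What to change.** Reconcile 3.4.1, 3.4.2, 3.7.1 (its heading and Table 3), 4.2.1.1 to 4.2.1.3 and Appendix A into one rule for the interval from birth to infant enrolment. It should cover nursing mothers, non-nursing mothers and formula-fed infants explicitly. Then make the dispensing lines in 4.2.1 and Appendix A match that rule, and align the timing of screening and enrolment between 3.4.2 and 4.2.1.3. State that Objective 2 compliance in this interval is judged against the reconciled rule. Which rule is right is for the sponsor to decide.

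The cost is amendment wording. If the reconciled rule requires earlier supply, some formula will be wasted in families later found HLA-ineligible, and the timing would have to fit the infant consent step that 4.2.1.2 places at the 2 to 28 day visit.
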